40. Schiff, D., et al., Phase 1 dose escalation trial of the safety and pharmacokinetics of cabozantinib concurrent with temozolomide and radiotherapy or temozolomide after radiotherapy in newly diagnosed patients with high-grade gliomas. *Cancer*, 2016. 122(4): p. 582-7.
doi:10.1097/CAD.000000000000108

APPENDIX A - DOSE MODIFICATION ALGORITHMS FOR POTENTIAL COMBINATION TREATMENT RELATED ADVERSE EVENTS

AE Terms & Descriptions	Dose Modification Algorithms
Diarrhea	
a. Grade 1-2 (duration < 48 hr)	a. Continue Cabozantinib at the current dose. If it does not improve with supportive measures consider a dose reduction. Continue temozolomide at the current dose.
b. Intolerable Grade 2 or Grade 3	b. Interrupt Cabozantinib and temozolomide until Grade ≤ 1 then consider restarting Cabozantinib at reduced dose. Dose reduce temozolomide by one dose level for Grade 3 only. Discontinue temozolomide for grade 4.
	c. Refer to the Table 0-3 for the management of diarrhea.
Neutropenia	
a. Neutrophil count <1.5	a. Interrupt temozolomide and cabozantinib until neutrophil count $\geq 1.5 \times 10^9/L$.
b. Neutrophil count <1.0	b. Interrupt temozolomide and cabozantinib until $\geq 1.5 \times 10^9/L$. Reduce temozolomide by 1 dose level. Continue cabozantinib at the same.
c. Neutrophil count <0.5	c. Discontinue temozolomide, interrupt cabozantinib until neutrophil count is $\geq 1.5 \times 10^9/L$ then resume at same dose.
Febrile Neutropenia	
Grade 3 or 4	Interrupt temozolomide and cabozantinib until resolved. Upon resumption, reduce temozolomide by 1 dose level. Continue cabozantinib at the same dose.
Thrombocytopenia	
Grade 1 or 2	Interrupt temozolomide until $\geq 100 \times 10^9/L$. Continue cabozantinib.
Grade 3 or 4	Interrupt temozolomide and cabozantinib until $\geq 100 \times 10^9/L$. Dose reduce temozolomide by 1 dose level. Continue cabozantinib at the same dose or reduce dose by one level-at the investigator's discretion. At platelet count of $< 10 \times 10^9/L$ discontinue temozolomide.

Hypertension	
> 140 mm Hg (systolic) ^a and < 160 mm Hg OR > 90 mm Hg (diastolic) and < 110 mm Hg	
 Optimize antihypertensive therapy. Reduce cabozantinib treatment by one dose level if optimal antihypertensive therapy (usually to include 3 agents) does not result in BP <140 mm Hg systolic or <90 mm Hg diastolic. Continue temozolomide at the current dose
≥ 160 mm Hg (systolic) OR ≥ 110 mm Hg (diastolic)	
 Reduce cabozantinib by one dose level or interrupt cabozantinib treatment per investigator discretion. Re-start cabozantinib treatment at the most tolerable dose and re-escalate only if BP falls to and is sustained at < 140 mm Hg systolic and < 90 mm Hg diastolic. 
Interrupt/continue temozolomide at the investigator's discretion.

Hypertensive emergency ^a	
 Discontinue cabozantinib treatment
^a Hypertensive emergency is defined as uncontrolled elevated BP with clinical evidence of progressive or impending end-organ damage (e.g. myocardial infarction/ischemia, intracranial hemorrhage, cerebral ischemia, pulmonary edema, encephalopathy, kidney damage).	
Hand-foot Syndrome (PPES)	
Grade 1	
 Cabozantinib treatment may be continued at the current dose if PPES is clinically insignificant and tolerable. Otherwise, cabozantinib should be reduced to the next lower dose level. ^a Start urea 20% cream twice daily AND clobetasol 0.05% cream once daily. 
Reassess at least weekly; if PPES worsens at any time or does not improve after 2 weeks, proceed to the intervention guidelines for Grade 2.
 
 Continue temozolomide at the current dose.

Grade 2	
 • Cabozantinib treatment may be continued if PPES is tolerated. • Cabozantinib should be dose reduced or interrupted if PPES is intolerable. • Continue urea 20% cream twice daily AND high potency steroid cream (e.g., clobetasol 0.05%) once daily and add analgesics (e.g., NSAIDs/gamma-aminobutyric acid agonists) for pain control if needed. 
Reassess at least weekly; if PPES worsens or affects self-care, proceed to the intervention guidelines for Grade 3.
 
 • Continue temozolomide at the investigator's discretion
Grade 3	
 • Interrupt cabozantinib treatment until severity decreases to Grade 1 or 0. • Continue treatment of skin reaction with high potency steroid cream (e.g., clobetasol 0.05%) twice daily AND analgesics. • Resume study drug at a reduced dose if PPES recovers to Grade ≤ 1. • Discontinue subject from study treatment if PPES does not improve within 6 weeks • Interrupt/continue temozolomide at the investigator's discretion
Proteinuria (UPCR)	
≤ 1 mg/mg (≤ 113.1 mg/mmol)	
 • No change in cabozantinib or temozolomide treatment
> 1 and < 3.5 mg/mg (> 113.1 and < 395.9 mg/mmol)	
 • Refer to Table 0-6 for the management of cabozantinib treatment. No change in temozolomide treatment
≥ 3.5 mg/mg (≥ 395.9 mg/mmol)	
 • Refer to Table 0-6 for the management of cabozantinib treatment. No change in temozolomide treatment.
Nephrotic syndrome	
 • Discontinue cabozantinib
Hepatocellular Toxicity	
Grade 2 AST or ALT or Total Bili lasting longer than a week	
 • Interrupt cabozantinib and temozolomide until Grade 1. • Refer to the Section 4.4.3.13 for the management of DILI
Other Treatment Related Adverse Events (such as fatigue, nausea, vomiting, anorexia, weight loss, etc)	

Grade 1 or Grade 2 (tolerable)	
 • Add supportive care as indicated. • Continue cabozantinib and temozolomide treatment at the current dose; monitor as clinically indicated
Intolerable Grade 2 or Grade 3	
 • Interrupt cabozantinib and temozolomide treatment until it is a Grade 1 or tolerable grade 2. Restart both cabozantinib and temozolomide at the current dose or dose reduced by one level.^b For Grade 3 AEs related to Temozolomide dose reduce by one level. • *Note: It is recommended that dose holds be as brief as possible
Grade 4-related to temozolomide Grade 4-related to cabozantinib (except clinically non-relevant laboratory abnormalities)	
 • Discontinue temozolomide. • Subjects should have cabozantinib interrupted immediately. • Discontinue cabozantinib unless the following criteria are met: Subject is deriving clear clinical benefit as determined by the investigator Toxicity can be managed with a dose reduction following recovery to Grade 1 (or baseline) and optimal medical care
Study treatment dose adjustment is only needed if the toxicity was deemed related to cabozantinib treatment or had an unclear relationship to cabozantinib treatment. ^b except nausea, vomiting, and alopecia- no dose interruption required for temozolomide	

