4.3 Treatment Administration

Agent	Dose	Route	Schedule	Cycle Length
Cabozantinib	40 mg (starting dose)	PO	QD	4 Weeks (28 days)
Temozolomide	150 mg/m ² (starting dose for Cycle 1), then 200 mg/m ² (Cycles 2+)	PO	QD Days 1-5 of each cycle	

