4.4.4 Management of Temozolomide Related Adverse Events

The most common adverse reactions ($\geq 10\%$ incidence) are: alopecia, fatigue, nausea, vomiting, headache, constipation, anorexia, convulsions, rash, hemiparesis, diarrhea, asthenia, fever, dizziness, coordination abnormal, viral infection, amnesia, and insomnia.

The most common Grade 3 to 4 hematologic laboratory abnormalities ($\geq 10\%$ incidence) that have developed during treatment with temozolomide are: lymphopenia, thrombocytopenia, neutropenia, and leukopenia.

Allergic reactions have also been reported.

Please refer to [Appendix A](#) for dose modification algorithms for potential combination treatment related adverse events.

Table 0-8: Temozolomide Dosing Interruption or Discontinuation during Treatment Period

Toxicity	Temozolomide Interruption	Temozolomide Discontinuation	Reduce Temozolomide by 1 Dose Level
Absolute Neutrophil Count (ANC)	≥ 0.5 and $< 1.5 \times 10^9/L$	$< 0.5 \times 10^9/L$	≥ 0.5 and $< 1.0 \times 10^9/L$
Platelet Count	≥ 10 and $< 100 \times 10^9/L$	$< 10 \times 10^9/L$	≥ 10 and $< 50 \times 10^9/L$
NCI-CTCAE non-hematological toxicity (except for alopecia, nausea and vomiting)	Grade 2	Grade 3 or 4	Grade 3

Treatment with temozolomide may be continued when all of the following conditions are met:

- $ANC \geq 1.5 \times 10^9/L$
- Platelet count $\geq 100 \times 10^9/L$
- NCI-CTCAE non-hematological toxicity \leq Grade 1 (except for alopecia, nausea and vomiting)

Table 0-9: Temozolomide Dose Levels

Dose 0 (Assigned Starting Dose)	Dose Level 1	Dose Level 0	Dose Level -1
150 mg/m ² /day	200 mg/m ² /day	150 mg/m ² /day	100 mg/m ² /day

Please see [Appendix B](#) for Daily Dose Calculations by Body Surface Area (BSA).

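### For febrile neutropenia with ANC below 0.5 x10^9/L, Appendix A lets temozolomide resume one level lower, while its own neutropenia row c and Table 0-8 discontinue it

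*Combined protocol and SAP*

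**What the plan says.** Three places give temozolomide instructions that apply to a subject with fever and a very low neutrophil count.

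- **Appendix A, febrile neutropenia, Grade 3 or 4.** The first action is "Interrupt temozolomide and cabozantinib until resolved". The second is "Upon resumption, reduce temozolomide by 1 dose level". Cabozantinib stays at the same dose. No ANC limit is given.
- **Appendix A, neutropenia row c (ANC below 0.5).** The action is "Discontinue temozolomide, interrupt cabozantinib until neutrophil count is" at least 1.5 x10^9/L, after which cabozantinib resumes at the same dose. Fever is not mentioned.
- **Section 4.4.4, Table 0-8** ("Temozolomide Dosing Interruption or Discontinuation during Treatment Period"). ANC below 0.5 x10^9/L sits in the discontinuation column. The one-level reduction column covers only ANC from 0.5 to below 1.0.

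Sections 4.4 and 4.4.4 refer the reader to Appendix A. Neither ranks the rows within the appendix, or the appendix against Table 0-8.

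**The concern.** Febrile neutropenia with ANC below 0.5 x10^9/L falls under two Appendix A rows that give different temozolomide instructions. One has the subject resume at a lower dose; the other stops the drug. A site that looks up the event by name finds the febrile row and an instruction about resuming. A site that looks up the count finds discontinuation.

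The stake is patient safety. Following the febrile row re-exposes a subject to temozolomide after severe neutropenia with fever, when the same count without fever ends temozolomide. Section 8.2.2 warns that temozolomide myelosuppression may lead to aplastic anemia, in some cases fatal. Section 4.4 acknowledges limited clinical experience with the combination, and Section 1.3 says the Cycle 1 temozolomide dose was modified because of observed toxicity. Several centers apply these tables, so handling could differ between them.

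**Working it through.** The check is mainly a comparison of text. Temozolomide instructions by ANC (x10^9/L) for a subject with Grade 3 or 4 febrile neutropenia:

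| ANC | Febrile neutropenia row | Neutropenia rows a to c | Table 0-8 |
|---|---|---|---|
| 0.5 to <1.0 | Interrupt, resume one level lower | Row b: interrupt, reduce one level | Interrupt, reduce one level |
| <0.5 | Interrupt, resume one level lower | Row c: discontinue | Discontinue |

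**Step 1: where the sources part.** At 0.5 to below 1.0 all three agree. Below 0.5, two say discontinue and one says resume lower. The documents do not define febrile neutropenia grades by ANC, and nothing keeps counts below 0.5 out of the febrile row, so the overlap is real.

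**Step 2: what differs in practice.** The immediate action is the same under both rows: temozolomide stops and cabozantinib is interrupted. Cabozantinib later resumes at the same dose under both. Only temozolomide after recovery differs.

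**Step 3: whether other text settles it.** Section 4.4.4 lists requirements under "Treatment with temozolomide may be continued when all of the following conditions are met": ANC at least 1.5, platelets at least 100, and non-hematological toxicity no worse than Grade 1. A subject who has recovered from an ANC below 0.5 can meet all three, so these do not prevent re-exposure. Section 4.4.3.15 discusses febrile neutropenia, but under cabozantinib management, and it gives no temozolomide dosing rule.

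**Step 4: how comparable rows are drafted.** The Grade 3 or 4 thrombocytopenia row reduces temozolomide one level and then adds a limit inside the row, beginning "At platelet count of", that discontinues it below 10 x10^9/L. The diarrhea entry reduces for Grade 3 and discontinues for Grade 4. The febrile neutropenia row covers Grade 4 but states no such limit.

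**Step 5: dose at stake per affected subject.** The levels come from "Table 0-9: Temozolomide Dose Levels" (200, 150 and 100 mg/m2/day) and the schedule from Section 4.3 ("QD Days 1-5 of each cycle").

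- Subject at 200: resumes at 150 mg/m2/day; 150 x 5 = 750 mg/m2 per course; 150/200 = 75% of the earlier dose.
- Subject at 150: resumes at 100 mg/m2/day; 100 x 5 = 500 mg/m2 per course; 100/150 = 67%.
- Subject at 100: Table 0-9 lists no lower level, so the febrile row names no dose to resume at.
- Under row c or Table 0-8: 0 mg/m2 in every case.

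**The case against.** The best defense is that the appendix already has to be read with the stricter row winning. Neutropenia rows a, b and c have no lower bounds, so an ANC of 0.4 literally meets all three, and everyone would still apply row c. Read the same way, the febrile row also yields to row c. Table 0-8 supports this by confining the one-level reduction to ANC of 0.5 and above. The words about resumption can also be taken as conditional: they set the dose if temozolomide restarts, while row c decides whether it does. The thrombocytopenia comparison is imperfect too, since that entry has no separate lowest-count row and neutropenia does.

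Much of this is fair, and it shows that a sensible reading leads to discontinuation. But that reading is unwritten. For rows a to c, Table 0-8 supplies explicit bounds; it has no febrile neutropenia row. A rule at least as natural, to follow the row that names the event, gives the opposite answer.

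Three limits on the concern stand. Neither row c nor Table 0-8 uses the word permanent, although the contrast with the interruption column implies it. Under the febrile row, temozolomide restarts only after the event resolves and at a reduced dose. And Section 4.8 requires an investigator to stop treatment for any adverse event judged to warrant it. These lessen the hazard; they do not remove the contradiction.

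**Conclusion.** The concern holds. For Grade 3 or 4 febrile neutropenia with ANC below 0.5 x10^9/L, the protocol gives two incompatible temozolomide instructions and no order of precedence. The more lenient one is attached to the sicker patient.

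The scope is narrow: one ANC range, one drug, and only dosing after recovery. Per affected subject the difference is 750 or 500 mg/m2 per course against none, assuming full five-day courses at the Table 0-9 levels. The documents give no rate of febrile neutropenia with ANC below 0.5, so no number of affected subjects is offered. The design's error rates and sample size do not depend on this point. It should be corrected as a safety matter.

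**What to change.** In the next amendment, put the ANC limit into the Appendix A febrile neutropenia row. Suggested wording: *If ANC was 0.5 x10^9/L or higher, resume temozolomide one dose level lower; if ANC was below 0.5 x10^9/L, discontinue temozolomide, as in neutropenia row c and Table 0-8.*

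The cost is one phrase in one row. Row c and Table 0-8 need no change for this point.

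A general statement that the strictest applicable rule governs would be a poor substitute. Table 0-8 lists Grade 3 non-hematological toxicity under both discontinuation and one-level reduction, so such a rule would turn those reductions into discontinuations and change dosing well beyond this case.

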4.4.3.6 Hypertension

Table 0-4 provides treatment guidelines for hypertension deemed related to cabozantinib.

Blood pressure should be monitored in a constant position visit to visit, either sitting or supine in a relaxed setting.

Decisions to reduce or interrupt the dose of study treatment must be based on BP readings taken by a medical professional and must be confirmed with a second measurement at least 5 minutes following the first measurement.

Cabozantinib should be discontinued in subjects with hypertensive emergency.

Table 0-4: Management of Hypertension Associated with Cabozantinib

Event	Management
Subjects NOT receiving optimized anti-hypertensive therapy	

> 140 mm Hg (systolic)^a and < 160 mm Hg
 
OR
 
> 90 mm Hg (diastolic) and < 110 mm Hg
	
 Optimize antihypertensive medications by adding new or additional antihypertensive medications and/or increase dose of existing medications. Reduce cabozantinib treatment by one dose level if optimal antihypertensive therapy (usually to include 3 agents) does not result in BP <140 mm Hg systolic or <90 mm Hg diastolic If subject is symptomatic interrupt cabozantinib treatment

≥ 160 mm Hg (systolic)
 
OR
 
≥ 110 mm Hg (diastolic)
	
 Reduce cabozantinib by one dose level^b or interrupt cabozantinib treatment per Investigator discretion. Add new or additional anti-hypertensive medications and/or increase dose of existing medications and monitor subject closely for hypotension. If optimized antihypertensive therapy (usually to include 3 agents) does not result in BP < 140 mm Hg systolic or < 90 mm Hg diastolic, cabozantinib treatment should be dose reduced further or interrupted. Cabozantinib treatment should be dose interrupted if upper limits of systolic BP (≥ 160 mm Hg) are sustained and not adequately manageable or if systolic BP is > 180 mm Hg or diastolic BP > 110 mm Hg, or if subject is symptomatic. Re-start cabozantinib treatment at the most tolerable dose and re-escalate only if BP falls to and is sustained at < 140 mm Hg systolic and < 90 mm Hg diastolic.
Hypertensive emergency ^c	
 Discontinue cabozantinib treatment.

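### The hypertension failure clause in Table 0-4 and Appendix A says 'or' where 'and' is needed, and Appendix A leaves out Table 0-4's interruption conditions without citing that table

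*Combined protocol and SAP*

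**What the plan says.** Table 0-4 in section 4.4.3.6 has two blood-pressure rows. The lower row applies when systolic pressure is above 140 and below 160, or diastolic is above 90 and below 110. The upper row applies when systolic is at least 160 or diastolic is at least 110. A separate row covers hypertensive emergency.

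In the lower row, Table 0-4 calls for optimized antihypertensive therapy, then a one-level reduction of cabozantinib if that therapy fails, and adds: "If subject is symptomatic interrupt cabozantinib treatment".

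In the upper row it starts with reduction or interruption at the investigator's discretion and then qualifies that in three ways:

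- Drug treatment for blood pressure is stepped up: "Add new or additional anti-hypertensive medications and/or increase dose of existing medications and monitor subject closely for hypotension".
- Where that does not bring control, the instruction is that "cabozantinib treatment should be dose reduced further or interrupted".
- A further bullet gives conditions for interruption alone. Its first condition concerns systolic pressure that stays high: "Cabozantinib treatment should be dose interrupted if upper limits of systolic BP (≥ 160 mm Hg) are sustained and not adequately manageable". Its remaining conditions are a set of higher readings and symptoms, so that the drug is also stopped "if systolic BP is > 180 mm Hg or diastolic BP > 110 mm Hg, or if subject is symptomatic".

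Appendix A, to which sections 4.4 and 4.4.4 refer for dose-modification algorithms, has the same two blood-pressure rows. Its lower row keeps the optimization and reduction steps. Its upper row says "Reduce cabozantinib by one dose level or interrupt cabozantinib treatment per investigator discretion" and gives a restart condition. Neither row cites Table 0-4 or section 4.4.3.6.

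The failure clause in the lower row of both tables is that therapy "does not result in BP <140 mm Hg systolic or <90 mm Hg diastolic". Table 0-4 repeats it in the upper row. The restart bullet in both tables instead says "re-escalate only if BP falls to and is sustained at < 140 mm Hg systolic and < 90 mm Hg diastolic".

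**The concern.** These rules tell an investigator when to lower or stop cabozantinib for a toxicity that section 4.4.3 lists among the events seen in at least 20% of subjects treated with the drug. Two things go wrong if the text is followed as it stands.

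First, the failure clause counts therapy as successful once either component is below target. A subject can enter a row on one raised component, stay raised on that component despite optimal therapy, and never reach the reduction or interruption step.

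Second, an investigator who works from Appendix A alone can continue cabozantinib at a reduced dose at pressures, or with symptoms, for which Table 0-4 directs interruption. Nothing in the Appendix A hypertension rows signals that stricter instructions exist.

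**Working it through.** No sample size, power or error rate is involved, so the plan has no figure to reproduce. The check is a truth table for the failure clause and a line-by-line comparison of the two tables. Each reading below is assumed to have been confirmed by a second measurement, as section 4.4.3.6 requires.

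**Step 1: the failure clause.** Write S for systolic and D for diastolic pressure on optimal therapy.

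- As written: NOT (S < 140 OR D < 90), which equals S ≥ 140 AND D ≥ 90.
- With 'and': NOT (S < 140 AND D < 90), which equals S ≥ 140 OR D ≥ 90.

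| Reading | Row | Triggers as written | Triggers with 'and' |
|---|---|---|---|
| 155/85 | lower | no | yes |
| 135/100 | lower | no | yes |
| 165/85 | upper | no | yes |
| 155/95 | lower | yes | yes |
| 130/80 | none | no | no |

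Three other places in the protocol show which version is meant:

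- The row criteria admit a subject on either component.
- Exclusion 8a defines uncontrolled hypertension as sustained pressure above 140 systolic or above 90 diastolic despite optimal treatment.
- The restart bullets require both components to be below target.

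The literal clause disagrees with all three, and the 'and' version fits them. The clause appears twice in Table 0-4 and once in Appendix A: 2 + 1 = 3 places.

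**Step 2: interruption conditions.** Table 0-4 has two bullets that direct interruption with no option to reduce instead, one in each row. Appendix A has neither.

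| Instruction | Table 0-4 | Appendix A |
|---|---|---|
| Lower row: interrupt if symptomatic | present | absent |
| Upper row: interrupt if S ≥ 160 is sustained and unmanageable, S > 180, D > 110, or symptomatic | present | absent |
| Upper row: add or increase antihypertensives | present | absent |
| Upper row: reduce further or interrupt if optimized therapy fails | present | absent |

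Applied to an asymptomatic subject on 40 mg whose upper-row reading is not sustained:

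| Reading | Table 0-4 | Appendix A alone |
|---|---|---|
| 185/115 | interrupt | 20 mg permitted |
| 182/100 | interrupt | 20 mg permitted |
| 170/112 | interrupt | 20 mg permitted |
| 165/95 | discretion | discretion |
| 160/110 | discretion | discretion |

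The 20 mg figure is the single reduction level in Table 0-1.

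**Step 3: does another rule close the gap?** The Grade 3 rule in Table 0-2 does not, because it also accepts a dose reduction where that manages the toxicity easily. Section 4.4 allows earlier reduction or interruption at the investigator's discretion but does not require it. Section 4.4.3 requires discontinuation for persistent uncontrolled hypertension despite optimal medical management. That rule covers part of the ground in Step 1, but it is a different action and does not supply the missing reduction step.

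**The case against.** The strongest reply is that the operative instructions are already in the protocol. Section 4.4.3.6 puts Table 0-4 in force for hypertension related to cabozantinib, and the footnote to Table 0-2 sends readers to section 4.4.3 for further instructions. Appendix A covers toxicities of the combination, and its hypertension rows add what to do with temozolomide. Its discretionary sentence is nearly the same as the opening of Table 0-4's upper row, so what is missing is the qualifiers. Interrupting the drug satisfies both texts. All of this stands. A reader might infer that Appendix A overrides Table 0-4 or contradicts it outright, and the documents do not support that.

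On the failure clause, it can be said that the row criteria and restart bullets make the intent plain, and that the discontinuation rule in section 4.4.3 is a backstop. If exclusion 8a's definition carries over, a subject persistently at 155/85 on optimal therapy would meet that stricter rule. This lowers the practical risk. It does not make the clause right: 'persistent' is not defined, and a graded step that should come into play is skipped.

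Hypertension might also be called the sole exception in Appendix A, since diarrhea and proteinuria point to their tables and hand-foot syndrome repeats its table's actions. That contrast should not be pressed. The hepatocellular entry has only a Grade 2 row, and it points to section 4.4.3.13 for drug-induced liver injury without naming Table 0-7.

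**Conclusion.** The point holds as a drafting fault in safety rules, wrong as written and worth correcting. Read literally, the failure clause gives the wrong action for isolated systolic or isolated diastolic hypertension on optimal therapy, in three places. Appendix A is an incomplete and more permissive summary of Table 0-4: both of that table's interruption bullets and two upper-row steps are missing, with no pointer to where they can be found.

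The first part rests on the literal reading of 'or'. The second rests on an investigator using Appendix A without also consulting section 4.4.3.6.

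A reader might go further and infer bias in the 12-week progression-free endpoint, or a count of subjects put at risk. The documents give no basis for either. A reader might also treat the absence of section 4.4.3's discontinuation rule from the two tables as a further defect. That rule is already in force, and repeating it there would put 'discontinue' beside 'reduce' with no stated order, so no change is recommended.

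**What to change.** 1. Change 'or' to 'and' between the two blood-pressure targets in the three failure clauses: both blood-pressure rows of Table 0-4 and the lower hypertension row of Appendix A.
2. In both Appendix A hypertension rows, add a reference to Table 0-4 for managing cabozantinib, in the form that the proteinuria rows already use for Table 0-6.

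The cost is three one-word changes and one line added to each of two rows. No visit, procedure or analysis changes.
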